. These late sequelae are chosen by reading results from a questionnaire about late sequelae fulfilled by members of: "Danish Network for Mouth and Throat Cancer" – a community of people who have been through treatment of cancer in throat and mouth.

Participants are also asked if they have any other late sequelae.

Third objective(side effects)

Participants are at the first treatment session receiving a diary to note if they have any side-effect after treatment. At each session the therapist will ask if the participant has been experiencing any side effects and these will be noted in the participant journal and combined together so that the results contain a total overview of experienced side effects

Intervention:

The participants will receive 50 minutes of treatment of craniosacral therapy once a week in 5 weeks. The treatment will follow the protocol "avenue of expression" and step 2c and 2c in "Ten step protocol". See appendix (1)

Statistical considerations

The participants filled in the danish questionaire " Xerostomia questionnaire after minimun 3 months". The questionnaire includes a VAS xerostomia scale 0-10 (10 is worst)

The remaining 14 questions were phrased "how much does [question subject] bother you:" (translated from Danish)

not at all (1) - a little (2) - some (3) a lot (4) very much(5)

The final question(number 15) were:

"How would you feel, if you had to live the rest of your life, with the symptoms you have now?:"
enjoyable(1), very satisfied (2) neither satisfied ore unsatisfied(3), very unsatisfied(4), terrible(5)
the sum of points from the 15 questions gives an overall score.

The remaining 14 questions were phrased "how much does [question subject] bother you:" (translated from Danish)

not at all (1) - a little (2) - some (3) a lot (4) very much(5)

The final question(number 15) were:

"How would you feel, if you had to live the rest of your life, with the symptoms you have now?:"
enjoyable(1), very satisfied (2) neither satisfied ore unsatisfied(3), very unsatisfied(4), terrible(5)
the sum of points from the 15 questions gives an overall score.

This will give two scores:

the was-scale-score between 0-10 (10 is worst)

and the score for the remaining questions between 15 – 75 (75 is best)

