The questionaire will be filled in on the treatmentday, before starting the treatment, on the 5.(and last time of treatment, before starting the treatment, and as a followingup, 6 month after the treatment. The participants will be alone, completing the questionnaire.

The result will be the participants' average score from the 3 times the questionnaire is completed. Averages will be calculated omitting missing values. Unfortunately, I have not been able to find information about, how large a change in the score there is clinically relevant.

Since there is no control group, I have decided that the participants must have completed the treatment at least two years before the start of the trial to ensure that any positive effects on xerostomia and the other side effects are not simply a result of natural healing. This choice was made on the basis of a systematic review of 1366 patients(10), where it is argued that it is probably

at least after 2 years after end of cancer-treatment that a relatively static state with regard to dry mouth occurs.

Because the intervention group is so small, and heterogeneous, when it comes to age, time since treatment, gender and cancer treatment methods results should be generalised to future patient populations with great caution.

During the calculation I have received supervision, from a colleague that has a lot of experience with statistics during research.

Participants:

Inclusion criteria

- More than 18 years, able to consent to participate.
- Have finished radiation treatment and/or surgery for oro-pharyngeal head or neck cancer at least two years before enrolling the project
- They shall score at least 4 on an xerostomia numeric scale where 0 is no xerostomia.

Exclusion criteria

- Persons who by surgery have got both their submandibular saliva glands removed.

And several contraindications:— see below:

- New case of cancer within a year
- Known to have an intracranial aneurysm or 2 close family members (parents, siblings, children) known to have aneurysm or bleeding under the brain.
- Perforation of the dura within a month
- Diagnosed bulge in the medulla oblongata
- History of traumatic neck or head injury that required hospitalization
- Planning to become pregnant, or pregnant before the twelfth week at the start of the project
- Signs of active disease - must be investigated by participant's own doctor first. Sorted out in

this project:

- radiation damage to the cervical vertebrae

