- If I during my journal procedure of my participant finds any signs of active disease, I will send them to their doctor and do not start my treatment before the doctors approval.

Risks, Side effects, disadvantages (long and short term)

Serious sideeffects of craniosacraltherapy is very seldom. When I was going to apply to "The central Denmark region Committees on health research ethics" for permission to carry out the project, they demanded a study of cases of serious side effects after craniosacral therapy, which made me make some extra exclusion criteria to this study. There is a single case where a person who was pregnant and had fallen had a spontaneous abortion after treatment. There are also a few cases where people who have been exposed to serious head or neck trauma have had side effects that required medical attention. Therefore, pregnancy and serious head/neck trauma are contraindicated in this project. In addition, there are a number of precautionary contraindications that are taken into account to avoid serious side effects. Read more under exclusion criteria.

Participants are instructed to contact their doctor if they experience anything concerning during the trial.

Any serious side effects will result in immediate cessation of the trial, and will of course be reported.

Commonly occurring/ not serious sideeffects

It is common for all types of patients to experience temporary fatigue, dizziness, flu symptoms, aches and pains, and increased digestive activity. It is also common to experience temporary emotional fluctuations. Since I have not treated many people with late effects of cancer, I do not know if they will have any other common late effects than the general population. Therefore it is a goal in this study to list any side-effects in this study.

Hygiene:

Since the participants belong to a group of people who are particularly vulnerable to infections and since the experiment was conducted during Covid times, face masks will be used during treatment and gloves are used when treating the mouth.

The table is disinfected between each treatment.

Gdpr

As this experiment takes place in Denmark, which is a member of the EU, there are a number of rules according to GDPR that must be observed. These are ensured in cooperation with "The central Denmark region Committees on health research ethics"

Economy:

sponsor/collaborators:

No sponsors - this study is self-financed

collaborators:

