Danish Cancer Society (has made treatment rooms available

DLHM - Danish Society for Mouth and Throat Cancer (recruitment of participants)

Danish Network for Mouth and Throat Cancer (recruitment of participants)

Recruitment of participants

I have contacted various relevant hospital departments and asked if they wanted to collaborate on recruiting participants, but they have not been interested.

Participants have received information about the possibility of participating in the project through presentations held in collaboration with:

DLHM - Danish Society for Mouth and Throat Cancer

and

Danish Network for Mouth and Throat Cancer

Informed consent

The participants have signed informed consent, which is based on templates developed by "The central Denmark region Committees on health research ethics". The information has been given both orally - via oral presentations - and in writing and contains everything the research ethics committee requires. They have also signed informed written consent, where they give permission for the

publication of the results. I have been in contact with employees from "The central Denmark region Committees on health on health research ethics", to make sure that this procedure has been done properly

Insurance

In the application procedure to the "The central Denmark region Committees on health research ethics", I had to ensure that the participants in the project are covered by my medical insurance. The participants are covered by my medical insurance

Publication of results:

The results will be published on clinicaltrials.gov. I will work to have the study published in a peer-reviewed journal – also in my professional journal (Danish physiotherapists) and on Upledger International's website (the institute that trains craniosacral therapists), where they have a subpage with links to various research. If the trial has positive results, I will communicate the results orally at relevant conferences/professional days or in patient associations. I will also make the results available on my own website.

Scientific ethics section

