Appendix section

Appendix 1

Treatment protocol Xerostomi

- anamnesis and introduction to the treatment. Here I made an oral agreement with the participant that they can ask me to stop the treatment at any time. I will also ask for consent to start the treatment in another bodily area than mentioned in the protocol, if I find that it is necessary.

Physical examination:

I will examine the cranial rhythm of heels, ankles, thighs, the pelvis, the ribbs, the shoulders, in the three global cranial hand positions, and the temporal hand position with a technique intended for listening for this rhythm.

I will do an arching to find energy cysts

All findings are documented in the journal.

Treatment

In every session I will start with a stillpoint at the feet.

I'll go through the protocol as far as I can during the time available, and continue in the next session.

Diaphragm with diaphragm handgrib

- diaphragm -

- Thoracic inlet
 - with diaphragm handgrib
- Infrathyroid muscles
 - with diaphragm handgrib
- os hyoideum and retrohyoid tissue
 - with diaphragm handgrib
- c1 og c2 (1 gram technique)
- treatment of the cranium in 5 steps:
 - 1: melt in the suboccipital tissue
 - 2: platform technique
 - 3: 5 grams traction of occiput in the direction of the cranium starting from atlas
 - 4 : decompression technique of the occipital condyles
 - 5: 5 grams dural traction

Cranial treatment

- frontal lift
- parietal lift
- sphenoidal compression-decompression

- temporal unilateral og bilateral ear-pull technique
- os mandibularis compression – decompression
- os nasalis technique
- os zygomaticus og processus pterygoideus – decompression techniques
- soft-tissue-technique upper and lower lip
- os maxillaris technique
- os vomer technique
- os palatinum technique
- roof of the mouth technique
- fascial glide of suprahyoid tissue
- tongue technique
- treatment of teeths and gums
- technique for re-stabilisation :
- Os maxillaris technique– in flexion and extension
- os mandibularis technique – compression and decompression
- os sphenoidalis technique – compression and decompression
- os temporale (earpull technique)
- cranial base technique

- CV4-technique

After each session I will retest the cranial rhythms . Test results and treatment is documented in the journal.

Finish the treatment with conversation, questions etc, and with information about expected side effects of the treatment.

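### The exclusion list bars pregnancy only when planned or before week 12, while the risk section contraindicates pregnancy without any gestational limit

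*Protocol*

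**What the plan says.** Two parts of the Protocol deal with pregnancy, and both are current text.

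- **Participants, Exclusion criteria.** The contraindications listed here include "Planning to become pregnant, or pregnant before the twelfth week at the start of the project". No other inclusion or exclusion criterion mentions pregnancy.
- **Risks, Side effects, disadvantages.** The author reports that the ethics committee required a study of serious side effects of craniosacral therapy, and that extra exclusion criteria followed from it. One finding is given as "There is a single case where a person who was pregnant and had fallen had a spontaneous abortion after treatment". The conclusion drawn is "Therefore, pregnancy and serious head/neck trauma are contraindicated in this project". The paragraph then mentions further precautionary contraindications and ends by referring the reader to the exclusion criteria.

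The other item in that conclusion, head or neck trauma, also has an entry in the list: "History of traumatic neck or head injury that required hospitalization".

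**The concern.** The exclusion list is what a participant is screened against, and the risk section explains why certain people must be kept out. Here the list is narrower than the explanation. It covers planned pregnancy and pregnancy before week 12 at the start, and is silent on week 12 onwards. The risk section covers pregnancy without qualification.

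What is at stake is participant safety, not inference. Pregnancy is one of the contraindications that the author derives directly from a reported adverse case, so the screening list should carry it out in full. The protocol also presents the pilot as a first step towards a larger randomised project. If this list were reused there by staff who had not written the risk section, the gap would matter more than it does now.

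**Working it through.** There is no figure to reproduce and no formula applies. The check sets the two statements side by side for each possible pregnancy status at the start of the project.

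| Status at the start | Exclusion criteria | Risk section |
|---|---|---|
| Planning to become pregnant | Excluded | Not mentioned |
| Pregnant, before week 12 | Excluded | Contraindicated |
| Pregnant, week 12 or later | Not listed | Contraindicated |

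**Step 1: does another criterion close the third row?** No. The remaining exclusions concern removal of both submandibular glands, new cancer, aneurysm, dural perforation, a bulge in the medulla oblongata, traumatic injury, signs of active disease and radiation damage to the cervical vertebrae. The inclusion criteria concern age and consent, time since cancer treatment and a minimum xerostomia score. None of these addresses pregnancy.

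**Step 2: does the stated rationale support a week-12 limit?** The risk section describes one case and gives no gestational week. The case neither supports nor contradicts a limit at week 12, and no other reason for that limit appears in the text.

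**Step 3: could the risk section be shorthand for the list?** It could. The closing pointer to the exclusion criteria favours this. It follows the sentence on precautionary contraindications and may refer mainly to those, but it can also be read as covering the whole paragraph. The trauma item gives limited evidence the other way. In the same sentence trauma carries a limiting word, and the list spells out a plausible meaning for it, namely injury that led to hospitalisation. Pregnancy carries no limiting word. This is a matter of judgement, because the protocol nowhere defines serious trauma as trauma that led to hospitalisation.

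**Step 4: does the shorthand reading remove the mismatch?** No. A reader who follows the pointer arrives at a narrower rule than the one just stated, with nothing to say which of the two is meant.

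**Step 5: how many people could be affected?** The document gives no sample size, ages, sex split or pregnancy count. The number is therefore an assumption: from zero to a few.

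**The case against.** The strongest reply is that the two statements can be applied together. The list gives grounds for exclusion and nowhere declares a later pregnancy eligible, and the risk section bars pregnancy outright. Jointly they exclude every pregnancy. This stands. A reader might infer that the protocol gives contradictory answers for the same person, or that it admits people at week 12 or later. The documents do not support either inference. The gap appears only when the list is used alone.

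A second reply is that a short label normally drops qualifiers, and that other limits in the list also come without a reason, such as a year for new cancer and a month for dural perforation. This stands in part. The missing reason does not show that the week-12 limit is wrong. The limit may be a deliberate early-pregnancy rule that came out of the study of side effects. Neither that study nor the committee's approval is in the text available here, so the documents do not show which of the two statements is the faulty one. Whichever it is, the two need to be brought into line.

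A third reply is that little depends on it in practice. The protocol is written in the first person by the therapist who also takes the history (Appendix 1: "anamnesis and introduction to the treatment"), so unknowing enrolment is unlikely. Past-tense wording under Hygiene ("since the experiment was conducted during Covid times") and Informed consent ("The participants have signed informed consent") suggests that recruitment may already be over. This also stands. It limits the importance of the point but does not remove the inconsistency.

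**Conclusion.** The point holds as a minor inconsistency in safety eligibility, worth considering. The list as worded would not by itself screen out a person at week 12 or later whom the risk section says should not be treated. That the wording differs is certain. What was intended is not, since the risk section may be a summary of the list.

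The effect is probably on few participants or none. This rests on two assumptions: pregnancy is uncommon among people at least two years past treatment for head or neck cancer, and the author applies both sections when taking the history. The primary endpoint, its analysis and its interpretation are untouched.

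A reader might go further and conclude that pregnant people were treated, or that treatment after week 12 is known to be harmful. Nothing in the protocol supports either conclusion.

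**What to change.** Use one pregnancy rule in both places.

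- **Default:** change the exclusion criterion to *pregnant (any week) or planning to become pregnant*. It then agrees with the risk section. This is the cautious choice while no reason for the week-12 limit is given.
- **If the limit was deliberate:** keep the criterion, and state the limit with its reason in the risk section.
- **If enrolment is complete:** leave the criterion as the historical record, and state in the report whether anyone pregnant was treated. Any successor protocol should carry the aligned wording.

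The cost is negligible: one line in the protocol, or one sentence in the report.

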Appendix section

Appendix 1

Treatment protocol Xerostomi

- anamnesis and introduction to the treatment. Here I made an oral agreement with the participant that they can ask me to stop the treatment at any time. I will also ask for consent to start the treatment in another bodily area than mentioned in the protocol, if I find that it is necessary.

Physical examination:

I will examine the cranial rhythm of heels, ankles, thighs, the pelvis, the ribbs, the shoulders, in the three global cranial hand positions, and the temporal hand position with a technique intended for listening for this rhythm.

I will do an arching to find energy cysts

All findings are documented in the journal.

Treatment

In every session I will start with a stillpoint at the feet.

I'll go through the protocol as far as I can during the time available, and continue in the next session.

Diaphragm with diaphragm handgrib

- diaphragm -

- Thoracic inlet
 - with diaphragm handgrib
- Infrathyroid muscles
 - with diaphragm handgrib
- os hyoideum and retrohyoid tissue
 - with diaphragm handgrib
- c1 og c2 (1 gram technique)
- treatment of the cranium in 5 steps:
 - 1: melt in the suboccipital tissue
 - 2: platform technique
 - 3: 5 grams traction of occiput in the direction of the cranium starting from atlas
 - 4 : decompression technique of the occipital condyles
 - 5: 5 grams dural traction

Cranial treatment

- frontal lift
- parietal lift
- sphenoidal compression-decompression

- temporal unilateral og bilateral ear-pull technique
- os mandibularis compression – decompression
- os nasalis technique
- os zygomaticus og processus pterygoideus – decompression techniques
- soft-tissue-technique upper and lower lip
- os maxillaris technique
- os vomer technique
- os palatinum technique
- roof of the mouth technique
- fascial glide of suprahyoid tissue
- tongue technique
- treatment of teeths and gums
- technique for re-stabilisation :
- Os maxillaris technique– in flexion and extension
- os mandibularis technique – compression and decompression
- os sphenoidalis technique – compression and decompression
- os temporale (earpull technique)
- cranial base technique

- CV4-technique

After each session I will retest the cranial rhythms . Test results and treatment is documented in the journal.

Finish the treatment with conversation, questions etc, and with information about expected side effects of the treatment.

